#### 10.1.9. Publication Policy

- The results of this study may be published or presented at scientific meetings. If this is foreseen, the Investigator agrees to submit all manuscripts or abstracts to 89bio before submission and only present or publish information after approval by 89bio. This allows 89bio to protect proprietary information and to provide comments.
- 89bio will comply with the requirements for publication of study results. In accordance with standard editorial and ethical practice, 89bio will generally support publication of multicenter studies only in their entirety and not as individual site data. In this case, a coordinating Investigator will be designated by mutual agreement.
- Authorship will be determined by mutual agreement and in line with the International Committee of Medical Journal Editors authorship requirements.

## **10.2.** Appendix 2: Clinical Laboratory Tests

- The clinical laboratory tests detailed in Table 6 will be performed by a central laboratory at timing/frequency detailed in the SoA (Table 2). Laboratory tests will be performed under fasting conditions (for at least 12 hours; it is recommended that subjects fast no more than 14 hours). Subjects should be instructed to attempt to remain consistent in how long they fast prior to blood draws for the duration of the study.
- Protocol-specific requirements for inclusion or exclusion of subjects are detailed in Section 5 of the protocol.
- Additional tests may be performed at any time during the study as determined necessary by the Investigator or required by local regulations.
- Investigators must document their review of each laboratory safety report.

**Table 6:** Protocol-Required Laboratory Assessments

| Hematology   |  |
|--|--|
| WBC with differential (Total   | RBC count                                  |
| Neutrophils, Lymphocytes, Monocytes, Eosinophils, Basophils – absolute and | RBC Indices:                               |
| %)   | MCV, MCH, MCHC, RDW, Reticulocyte count    |
| Hemoglobin   | Hematocrit                                 |
| Platelet count   | Coagulation panel, including PT, INR, aPTT |
| Lipid Assessment   |  |
|  | non-HDL-C*                                 |
| ApoB*  | RLP-C*                                     |
|  |  |
| HDL-C*   | TG*  |
|  | VLDL-C*                                    |
| LDL-C*   | VLDL-TG*                                   |
|  |  |
| Clinical Chemistries   |  |
| ALP  | Fasting plasma glucose                     |
| ALT  | GGT  |
| AST  | Lactate dehydrogenase                      |
| Albumin  | Magnesium                                  |
| Bicarbonate  | Phosphorus                                 |
| BUN  | Potassium                                  |
| Calcium  | Sodium                                     |

| Creatinine, eGFR   | Total bilirubin, Indirect/direct bilirubin   |
|--|--|
| CK   | Total protein  |
| Chloride   | Uric acid  |
| Urinalysis   |  |
| Basic urinalysis (dipstick, including macroscopic appearance, bilirubin, blood, color, glucose, ketones, leukocyte esterase, nitrite, pH, protein, specific gravity, urobilinogen);  | Full urinalysis (dipstick plus microscopic evaluation) to be performed only at the screening and End of Study visits). A reflex microscopic urinalysis should be performed if the results of the urinalysis are abnormal or at the discretion of the PI or delegate. |
| Other Study-Specific Laboratory
Assessments   |  |
| BIO89-100 (to be evaluated by bioanalytical laboratory) Thyroid function assessment (TSH, free T4, and free T3)  |  |
| Serum hCG pregnancy test Urine hCG pregnancy test # FSH level   |  |
| Urine drug screen including
amphetamines, barbiturates, cocaine
metabolites, opiates, benzodiazepines,
cannabinoids and phencyclidine   |  |
| Serology – HIV antibody, hepatitis B surface antigen (HBsAg, and HCV antibody). To determine current infection status, if HBsAg positive HBV DNA will be measured, if HCV antibody positive, HCV RNA will be measured, and if HIV antibody positive will be differentiated by HIV 1 or 2 and HIV RNA will be measured. |  |
| 24-hour urine for cortisol and creatinine  Insulin   |  |
| hsCRP  |  |
| Serum adiponectin, total   |  |

\* Post-baseline lipid panels to be blinded # Tests can be performed locally with kits provided by the central laboratory Abbreviations: ALP = alkaline phosphatase; ALT = alanine aminotransferase; ApoB = apolipoprotein B100; ; aPTT = activated partial thromboplastin time; AST = aspartate aminotransferase;: BUN = blood urea nitrogen: CK = creatine ; DNA = deoxyribonucleic acid; eGFR = estimated kinase; glomerular filtration rate using CKD-EPI (Chronic Kidney Disease Epidemiology Collaboration) equation; ; FSH = follicle-stimulating hormone; GGT = gamma-glutamyl transferase; HBsAg = Hepatitis B surface antigen; ; HBV = Hepatitis B virus; hCG = human chorionic gonadotropin; HCV = Hepatitis C Virus; HDL-C = high-density lipoprotein-cholesterol; HIV = human immunodeficiency virus; ; INR = international normalized ratio; LDL-C = lipoprotein-cholesterol; ; MCH = mean corpuscular hemoglobin; MCHC = mean corpuscular hemoglobin concentration; PT = prothrombin time; PINP = n-terminal propeptide of type I procollagen; MCV = Mean Corpuscular Volume; Non-HDL-C = non-high-density lipoprotein-cholesterol; RBC = red blood cell; RDW = Red Cell Distribution Width; RLP-C = remnant lipoprotein-cholesterol; RNA = ribonucleic acid; T3 = triiodothyronine; T4 = thyroxine; : TG = triglycerides; TSH = thyroid-stimulating hormone; VLDL-C = very low-density lipoprotein cholesterol; VLDL-TG = very low-density lipoprotein triglycerides; WBC = white blood cell.

## 10.3. Appendix 3: Adverse Events: Definitions and Procedures for Recording, Evaluating, Follow-up, and Reporting

#### **10.3.1. Definition of AE**

#### **AE Definition**

- An AE is any untoward medical occurrence in a clinical study subject, temporally associated with the use of IP, whether or not considered related to the IP.
- NOTE: An AE can, therefore, be any unfavorable and unintended sign (including an abnormal laboratory finding), symptom, or disease (new or exacerbated) temporally associated with the use of IP.

#### **Events Meeting the AE Definition**

- Any abnormal laboratory test results (hematology, clinical chemistry, or urinalysis) or other safety assessments (e.g., ECG, radiological scans, vital signs measurements), including those that worsen from baseline are considered clinically significant in the medical and scientific judgment of the Investigator (i.e., not related to progression of underlying disease).
- Exacerbation of a chronic or intermittent pre-existing condition including either an increase in frequency and/or intensity of the condition.
- New conditions detected or diagnosed after IP administration even though it may have been present before the start of the study.
- Signs, symptoms, or the clinical sequelae of a suspected drug-drug interaction.
- Signs, symptoms, or the clinical sequelae of a suspected overdose of either IP or a concomitant medication. Overdose per se will not be reported as an AE/SAE unless it is an intentional overdose taken with possible suicidal/self-harming intent. Such overdoses should be reported regardless of sequelae.

#### **Events NOT Meeting the AE Definition**

- Any clinically significant abnormal laboratory findings or other abnormal safety assessments which
  are associated with the underlying disease, unless judged by the Investigator to be more severe than
  expected for the subject's condition.
- The disease/disorder being studied or expected progression, signs, or symptoms of the disease/disorder being studied, unless more severe than expected for the subject's condition.
- Medical or surgical procedure (e.g., endoscopy, appendectomy): the condition that leads to the procedure is the AE.
- Situations in which an untoward medical occurrence did not occur (social and/or convenience admission to a hospital).
- Anticipated day-to-day fluctuations of pre-existing disease(s) or condition(s) present or detected at the start of the study that do not worsen.

#### 10.3.2. Definition of Suspected and Unsuspected Adverse Reaction

#### Suspected adverse reactions are defined as:

 Any AE for which there is a reasonable possibility that the IP caused the AE. For the purposes of 89bio regulatory safety reporting, "reasonable possibility" means there is evidence to suggest a causal relationship between the IP and the AE. A suspected adverse reaction implies a lesser degree of certainty about causality than adverse reaction, which means any AE caused by an IP

#### **Unexpected AEs are defined as:**

• AE which is not listed in the IB of the IP or is not listed at the specificity or severity that has been observed

#### **10.3.3.** Definition of Events to Monitor

#### 89bio-defined Events to Monitor for BIO89-100:

Events to Monitor include hypersensitivity reactions occurring after the first administration of study agent(s) in subjects participating in this clinical study. These events must be reported by the Investigator to 89bio within 24 hours and are to be considered serious (for regulatory reporting purposes) only if they meet the definition of an SAE. The events are to be reported on an SAE form

#### 10.3.4. Definition of SAE

If an event is not an AE per definition in Section 10.3.1, then it cannot be an SAE even if serious conditions are met (e.g., hospitalization for signs/symptoms of the disease under study, death due to progression of disease).

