### 2. INTRODUCTION

# 2.1. Study Rationale

BIO89-100 is a glycoPEGylated analog of FGF21, a metabolic hormone, regulated by nutritional status, that affects energy expenditure and glucose and lipid metabolism. It is secreted mainly by the liver, but also by white adipose tissue, skeletal muscle, and the pancreas. The activation of FGFRs by FGF21 requires the transmembrane protein cofactor β-Klotho, expressed predominantly in metabolic organs, including the liver, white adipose tissue, and the pancreas, conferring organ specificity to FGF21 (Li, et al. 2015; Ogawa, et al. 2007). Administration of exogenous FGF21 is being explored as a method to treat hypertriglyceridemia, which is associated with increased risk of AP and CVD. Severe hypertriglyceridemia, defined as fasting TG levels of greater than or equal to 500 mg/dL, is associated with an increased risk of AP, accounting for up to 10% of all AP episodes (de Pretis, 2018), and an increased risk of NAFLD, NASH, and CVD (Grundy, et al. 2019). Clinical practice guidelines from both the American College of Cardiology/American Heart Association and from the American Association of Clinical Endocrinologists/American College of Endocrinology emphasize the importance of reducing TG in patients with levels above 500 mg/dL. Current treatments for hypertriglyceridemia include fibrates, fish oils, niacin, and statins. While currently approved therapies are proven to reduce TG levels, the treatment goal of alleviating SHTG, i.e., reducing TG levels to below 500 mg/dL remains a significant challenge. In the Phase 3 studies with Vascepa® and Epanova®, ~50% of subjects did not have TG level reductions below 500 mg/dL at the end of the 12-week studies (Chowdhury, 2012, Chowdhury 2014). Patients with TG levels above 500 mg/dL remain at risk for AP as well as cardiovascular and fatty liver diseases. Several non-clinical and clinical studies have shown that administration of various FGF21 analogs had beneficial effects on serum lipid and insulin-resistance as well as on liver fat (Zhang, et al. 2014, Gaich, et al. 2013, Sanyal, et al. 2018). A PD effect of BIO89-100 on TGs has been demonstrated, with significant reductions in TG levels in a non-human primate disease model and in the Phase 1a clinical study, TV47948-SAD-10122.

In Part 1 of the Phase 1b/2a

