# 2.2. Background

## 2.2.1. Severe Hypertriglyceridemia

Hypertriglyceridemia refers to elevated TG concentrations in the blood, usually measured after fasting but occasionally non-fasting. High TGs are defined as TG = 200 to 499 mg/dL and very high triglycerides, or SHTG as TG ≥500 mg/dL (Berglund, et al. 2012; Jellinger, et al. 2017). Subjects with elevated levels of serum TGs (≥500 mg/dL) are at increased risk of AP, NASH, NAFLD and CVD (Grundy, et al. 2019). Persistent hypertriglyceridemia is associated with the development of AP and CVD. For example, people with high versus low, non-fasting TG (580 mg/dL vs 70 mg/dL) were at 5.1-fold higher risk for myocardial infarction, 3.2-fold higher risk of ischemic heart disease, 3.2-fold higher risk for ischemic stroke, and 2.2-fold higher risk for all-cause mortality (Nordestgaard, 2016). Patients with SHTG are at increased risk of AP with a reported 5% and 10% to 20% lifetime risk of AP in patients with TG >1000 and >2000 mg/dL respectively (Blom, et al. 2018, Scherer, et al. 2014). Kiss et al., reported that elevated TG worsens the severity of AP and increases the risk for local and systemic complications, however, they reported no specific correlation of AP severity with extent of hypertriglyceridemia (Kiss, et al. 2018). The mechanisms by which SHTG causes pancreatitis are not fully understood but may relate to impairment of capillary perfusion in the pancreas, pancreatic cell necrosis and subsequent release and activation of pancreatic enzymes (Blom, et al. 2018). If and when pancreatitis will occur in an individual patient is unpredictable. Episodes of acutely-elevated TG levels, associated for instance with alcohol use or meals with excessive fat, could increase risk in patients with chronically high TG levels. In most patients who develop AP secondary to SHTG, the condition is mild and self-limiting, but ~20% of patients suffer severe attacks associated with prolonged hospitalization and significant morbidity and mortality.

Given the high risk of AP associated with SHTG, early diagnosis is essential so that treatment can be initiated, including simple carbohydrate- and fat-restricted diet, use of medium-chain TG-rich foods and alcohol abstinence (Berglund, et al. 2012; Jacobson, et al. 2015).

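### The protocol's AE and SAE definitions allow two readings for acute pancreatitis, one of which lets a pancreatitis admission or death go unrecorded

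*Protocol*

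**What the plan says.** Four parts of the protocol bear on how an on-study pancreatitis is recorded.

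- **The AE exclusion.** Section 10.3.1, under events not meeting the AE definition, lists "The disease/disorder being studied or expected progression, signs, or symptoms of the disease/disorder being studied, unless more severe than expected for the subject's condition".
- **The SAE consequence.** Section 10.3.4 says that an event outside the AE definition cannot be an SAE even when serious conditions are met. Its examples are "hospitalization for signs/symptoms of the disease under study, death due to progression of disease".
- **The link to the disease.** Section 2.1 says that SHTG "is associated with an increased risk of AP, accounting for up to 10% of all AP episodes". Section 2.2.1 goes further: "The mechanisms by which SHTG causes pancreatitis are not fully understood". It adds that most such attacks are mild, but that about "20% of patients suffer severe attacks associated with prolonged hospitalization and significant morbidity and mortality".
- **The rule that points the other way.** Section 10.3.1, under events meeting the AE definition, includes conditions newly detected or diagnosed after IP administration. Exclusion criterion 6 in Section 5.2 lists pancreatitis within 5 years of screening.

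The Events to Monitor in Section 10.3.3 name hypersensitivity reactions only. SAP 5.9 restates the AE and SAE definitions without the disease-under-study exclusion. SAP 7.6.1 builds its tables and listings from events recorded as AEs.

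**The concern.** AP is the acute event that the protocol itself uses to explain why SHTG needs treatment. It is also the event for which the disease-under-study exclusion is most ambiguous. An investigator who reads Sections 2.2.1, 10.3.1 and 10.3.4 together can conclude that an AP admission is a manifestation of SHTG and therefore neither an AE nor an SAE. Another investigator, applying the new-condition rule, would record the same event.

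Recording would then depend on the site. An event left out at that stage would miss the 24-hour SAE report in Section 8.3.1 and every SAP safety table and listing. The trial has no data monitoring committee (Protocol 9.6), although a committee would in any case see only what had been recorded. An unrecorded case on active drug would hide a possible harm. An unrecorded case on placebo would hide evidence relevant to benefit.

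**Working it through.** The documents give no figure for this point, so the main check is to set the rules side by side for one case: a subject with no pancreatitis in the past 5 years who is admitted with AP during treatment.

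| Rule | Reading A: record it | Reading B: do not record it |
|---|---|---|
| New conditions after IP (10.3.1) | AP is new, so it is an AE | Not stated to override the exclusion |
| Disease under study (10.3.1) | AP is a complication, not a sign or progression of SHTG | 2.2.1 says SHTG causes pancreatitis, so AP can be called disease-related |
| More severe than expected (10.3.1) | An admission exceeds what was expected for this subject | No reference severity is given; 2.2.1 describes hospitalization as part of severe attacks |
| SAE rule (10.3.4) | Hospitalization makes the AE serious | Not an AE, so not an SAE despite hospitalization or death |

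Both columns can be followed without breaking a written rule, and no readable sentence says which prevails.

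**How much one case matters.** This is an illustration only. The documents give lifetime AP risks (5% for TG above 1000 mg/dL, 10% to 20% above 2000 mg/dL) and no on-study risk, so the per-subject risk p is an assumption, taken from 0.1% to 2%. Planned n = 90 + 36 = 126 (Protocol 1.1).

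- Expected events = n × p
- P(at least one) = 1 − (1 − p)^n
- P(exactly one) = n × p × (1 − p)^(n − 1)

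| Assumed p | Expected events, n = 126 | P(at least one) | P(exactly one) | Share of trials with any AP that have exactly one |
|---|---|---|---|---|
| 0.1% | 0.13 | 11.8% | 11.1% | 94% |
| 0.5% | 0.63 | 46.8% | 33.7% | 72% |
| 1% | 1.26 | 71.8% | 35.9% | 50% |
| 2% | 2.52 | 92.2% | 20.2% | 22% |

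The last column is P(exactly one) divided by P(at least one). For p = 0.5%: 0.337 / 0.468 = 0.72.

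SAP 5.5 describes fibrate-cohort enrolment as low, so the true total is probably below 126. With the main cohort alone (n = 90), expected events are 0.09, 0.45, 0.90 and 1.80, and P(at least one) is 8.6%, 36.3%, 59.5% and 83.8%.

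For assumed risks up to 1%, at least about half of the trials with any AP would have a single case. One decision not to record it would then turn a count of one into zero.

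**The case against.** The strongest reply is that the protocol already captures AP. The new-condition rule sits in the same section as the exclusion. Exclusion criterion 6 makes an on-study attack a new event for most subjects. SHTG is defined biochemically, AP is never called a sign, symptom or progression of it, and Section 2.2.1 says that its occurrence in an individual is unpredictable, which fits poorly with expected progression. Section 8 also sends immediate safety concerns to the Medical Monitor. All of this stands, and it is why many investigators would record AP. It does not settle the matter, because no sentence ranks the two rules and 10.3.4 expressly contemplates unreported hospitalization and death.

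A second reply is that much of Protocol 2.3.1 and several SAP sections are not readable in the public text and may address AP. That is fair, so the point rests on the written exclusion and not on any missing AP-specific procedure.

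Four stronger readings are tempting, and the documents do not support them.

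- **That the severity clause is the only way out of the exclusion.** The new-condition rule is another.
- **That events would be lost selectively by arm.** Subjects, investigators and sponsor are blinded to treatment, and post-baseline lipids are blinded too (Protocol 6.4). No mechanism for differential loss is visible.
- **That cardiovascular events are equally exposed.** Section 2.2.1 says "Persistent hypertriglyceridemia is associated with the development of AP and CVD", but that is an association. No passage treats cardiovascular events as progression of SHTG.
- **That a confidence limit on AP incidence measures the problem.** With 72 + 18 = 90 planned on active drug and no events, the one-sided 95% upper limit is 1 − 0.05^(1/90) = 3.3%. That describes the sample size. It says nothing about how often AP would be misclassified.

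**Conclusion.** The point holds in a limited form. Sections 10.3.1 and 10.3.4 contain a stated rule, not merely a silence, under which an AP admission or death may be classed as disease-related and left unrecorded. A competing rule in 10.3.1 would capture it, and the protocol does not say which governs. It does not follow that AP will be lost, only that recording may vary with the investigator and that no SAP output would reveal an omission.

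The likelihood of misclassification cannot be estimated from the documents. The consequence can be bounded only under assumed risks: about 0.1 to 2.5 expected cases among 126 planned subjects, so a single omission could remove the whole AP count. The effect is under-counting, with no evidence of a difference between arms. This is an inexpensive clarification that protects safety ascertainment; it does not affect the primary analysis.

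**What to change.** Reconcile the two lists in 10.3.1 with 10.3.4 by adding to both sections: *Acute pancreatitis is always recorded as an AE, and as an SAE when a seriousness criterion is met, regardless of its relation to SHTG; the disease-under-study exclusion does not apply to it.* Align SAP 5.9 with the clarified definition. Deleting the examples from 10.3.4 would not be enough, because the exclusion in 10.3.1 and the sentence that a non-AE cannot be an SAE would remain in force.

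If enrolment is already complete, an amendment will come too late to affect collection. In that case, query all sites before database lock for any unrecorded pancreatitis and any related hospitalization or death, while treatment is still blinded, and enter what is found.

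The cost is one amendment sentence or site letter, or one round of queries, and possibly a few more reported events. No visit, procedure, dose or treatment rule changes.

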#### An SAE is defined as any untoward medical occurrence that, at any dose:

- 1. Results in death
- 2. Is life-threatening

#### An SAE is defined as any untoward medical occurrence that, at any dose:

The term 'life-threatening' in the definition of 'serious' refers to an event in which the subject was at risk of death at the time of the event. It does not refer to an event, which hypothetically might have caused death, if it were more severe.

#### 3. Requires inpatient hospitalization or prolongation of existing hospitalization

In general, hospitalization signifies that the subject has been detained (usually involving at least an overnight stay) at the hospital or emergency ward for observation and/or treatment that would not have been appropriate in the physician's office or outpatient setting. Complications that occur during hospitalization are AEs. If a complication prolongs hospitalization or fulfills any other serious criteria, the event is serious. When in doubt as to whether "hospitalization" occurred or was necessary, the AE should be considered serious.

Hospitalization for elective treatment of a pre-existing condition that did not worsen from baseline is not considered an AE.

